1) We will maintain communication. Specifically, the research coordinator will be in constant communication with participants. The coordinator will ensure the eligibility of the participant, safety of the participant, adherence to tasks, and contentment of the participant, throughout the study duration. The coordinator will explain all expectations and study details and re-explain throughout the study duration. In addition, upcoming visits will be reminded through phone calls or other communication methods of each participant's preference. Change of schedule will also be accommodated and coordinated by the study coordinator. 2) Participants' time and effort spent on research will be remunerated by the participation payment according to the payment schedule. 3) To maximize participants' convenience, a waiting area is provided in the lobby of the CBI with convenient access to the restrooms. Participants' parking is also accommodated in a parking lot adjacent to the research building. 4) We will ensure that our staff is well educated about the protocol and procedures by training and observing all procedures at least quarterly.

Staff Safety Training.

All research staff personnel will successfully complete IRB Certification training (CITI and GCP certification) and will be as forthcoming as possible with participants. Additionally, research staff will receive safety training in MRI by Center for Biomedical Imaging staff at MUSC.

Confidentiality.

All data except for the consent forms and HIPAA forms will be de-identified at the time of data recording. All electronic data will be stored in a password-protected research server that is accessible to study personnel only. The server is backed up every day and maintained 24/7 by IT specialists. All paper data with personally identifiable information including the consent forms and HIPAA forms will be stored in a key-locked cabinet in a key-locked room that is accessible to the study personnel only. Other paper data without personally identifiable information including testing sheets documenting testing sequences and notes will also be stored in a cabinet in a key-locked room that is accessible to study personnel only.

Screening Measures & Emergency Room.

Participants will be thoroughly screened for MRI eligibility multiple times (initial phone contact, intake interview, and again at each MRI scanning session). In the event of adverse effects related to MRI scanning, safety coordinators and medical staff have been trained how to quickly address any emergencies that may arise.

Close monitoring of participant stress and wellbeing will take place over all experimental sessions.

Physiological Recording Equipment.

Physiological recording devices meet all standards for non-invasive, scanner compatible materials.

Incidental findings

Incidental findings that may be uncovered from the MRI scan will be communicated directly to the participant immediately as they are found and explained by the investigator.

E3. POTENTIAL BENEFITS OF THE PROPOSED RESEARCH TO THE SUBJECTS AND OTHERS

There may be no direct benefits from participating in this study.

E4. IMPORTANCE OF THE KNOWLEDGE TO BE GAINED

With the precautions in place to select participants, we expect a very low risk of adverse events in our proposed participant cohort. This is relative to the substantial benefit in better understanding the effect of a focal lesion on neural network dynamics during sensorimotor learning in chronic stroke. Thus, the potential benefits for basic research and the expected findings' implications for the future design of targeted treatment for post-stroke sensorimotor rehabilitation likely outweighs the mild discomfort, risks of more serious outcomes, and time spent by participants enrolled in the proposed research.

E5. SUBJECT SAFETY AND MINIMIZING RISKS (Data and Safety Monitoring Plan)

E5.1 Safety Training.

The applicant along with the research assistant assisting with the scans will have taken first aid and CPR certification courses to assess and respond to participant emergencies within and outside of the scanner before beginning the study. Before any investigator or assistant is allowed to enter the scanner room, they are required to take an extensive MRI safety course (with annual refresher courses) that cover powering down (or quenching) the magnet for patient safety and with established procedures for expediting participant contact with emergency medical personnel, should the need arise. These courses are run by the MUSC Center for Biomedical Imaging and are a prerequisite for obtaining privileges to book and use scanner time.

E5.2 Medical Emergencies.

Emergency responding in the scanner is facilitated by having at least two research staff running a scan (applicant and research assistant as well as the MR technologist). In the event of an emergency, one of these individuals remains with the participant and undocks the scanner bed from the magnet bore. This bed can easily be wheeled out of the scan room to facilitate speedy access to arriving emergency medical personnel. The second researcher calls 9-1-1 from the scanner suite and gives details of the participant's level of medical distress and location. Next, this person goes out to the front of the scanner building to flag down arriving emergency personnel and to direct them to the participant. These guidelines are in full agreement with Center for Biomedical Imaging safety protocols.

E5.3 Ethical Research Practices.

Ethical guidelines for clinical research will be followed strictly and all information obtained in the study will be kept strictly confidential. The PI and all research staff and mentors will be responsible for and will comply with mandated reporting rules. All researchers will be obligated to demonstrate that they have remained abreast of all guidelines and rules related to the Health Insurance Portability and Accountability Act (HIPAA). Each member of the research staff will complete focused training on each task for which they are responsible and will perform ongoing quality control for others performing similar work.

E5.4 Data Monitoring Procedures.

The PI and/or study coordinator will produce quarterly administrative reports describing study progress including accrual, demographics, and participants' status. Reports will describe adherence to inclusion/exclusion criteria and the study protocol in addition to any unanticipated problems in the category of risks to participants or others as well

as any adverse events. All collected data will be obtained for research (and participant safety) purposes only. MRI data will be processed biweekly to entail consistent quality and scanner characteristics.

E5.5 Data and Safety Monitoring Board.

Data will be monitored on a bi-annual basis with respect to subject safety issues throughout the award period. The data and safety monitoring plan will include an internal Data Safety Monitoring Committee (DSMC), an external Data and Safety Monitoring Board (DSMB), and the Institutional IRB. The purpose of the DSMC, DSMB, and IRB are to ensure the safety of participants and the validity and integrity of the data.

E5.6 Data Safety Monitoring Committee (DSMC).

The internal DSMC will consist of the PI and co-investigators/consultants on the proposal. The functions of the DSMC will include: 1) providing scientific oversight; 2) reviewing all adverse effects or complications related to the study; 3) monitoring enrollment; 4) reviewing summary reports relating to compliance with protocol requirements; and 5) providing advice on resource allocation. The DSMC will meet quarterly and as necessary by telephone. The recommendations of the DSMC will be reviewed and the PI will take appropriate corrective actions as needed.

E5.7 Data and Safety Monitoring Board (DSMB).

A DSMB will be established and will consist of professionals at MUSC with appropriate expertise, who are willing to participate and who do not have any conflicts of interest. The DSMB will include: 1) one expert in the area of MR imaging, 2) a physician with expertise in chronic stroke, 3) a stroke rehabilitation specialist (physical or occupational therapist). The DSMB will meet on an annual basis. The DSMB will perform the following activities:

- Review the research protocol and plans for data and safety monitoring.
- Evaluate the progress of the intervention, including periodic assessments of data quality and timeliness, participant recruitment, enrollment, and retention, participant risk versus benefit, integrity of the intervention, and other factors that can affect study outcome.
- Consider factors external to the study when interpreting the data, such as scientific or clinical developments that may impact the safety of study participants or the ethics of the study.
- Make recommendations to the internal DSMC and MUSC IRB for continuation or termination of the project.
- Protect the confidentiality of study data and monitoring.

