We still do not know enough about how a focal lesion impacts the dynamics within brain circuits that govern motor learning and how this relates to maladaptive plastic changes. Filling this knowledge gap builds the basis for designing interventions that causally target experience-dependent maladaptive changes which negatively impact the patient's recovery (e.g., leading to disuse of the paretic hand). With this JI project, we will generate pilot data serving as the first evidence for motor learning-related network dynamics in the chronic phase after stroke (aim 1) and their link with biomarkers of recovery of upper-extremity sensorimotor function (aim 2).

AIM 1 To characterize motor learning (ML)-related neural network dynamics in the presence of a focal lesion, we will use a representational statistical modeling approach¹⁸ to describe learning-related connectivity changes based on task-based functional magnetic resonance imaging (fMRI) in stroke survivors (≥ 6 months post-lesion, stroke group SG) and healthy volunteers of comparable age and gender (control group, CG). Functional connectivity patterns will be modeled throughout the acquisition phase to capture the temporal trajectory of encoding-related network changes.

AIM 2 To understand the association between ML-related network dynamics and biomarkers of recovery, we will comprehensively describe upper-extremity sensorimotor functioning and impairment for the individuals in the SG and statistically integrate these biomarkers of recovery with the ML-related network dynamics within a separate representational model.

B. BACKGROUND AND SIGNIFICANCE

Recovery of upper extremity function remains dissatisfying for the majority of stroke survivors with sensorimotor impairment¹⁹, which represents a major hindrance to independence in daily life²⁰. Within the field of rehabilitation research, learning mechanisms have long been a major area of interest because they are considered one key player in functional recovery. This basic premise goes back to seminal work that established the brain's capacity to change in response to environmental stimuli and learning, i.e., experience-dependent plasticity^{21,22}.

However, it is evident that plasticity does not have purely beneficial effects on recovery³ but that also negative consequences such as learned disuse of the paretic hand can be observed¹.

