Imaging Parameters (sessions 3 and 4). Scanning will take place at the Center for Biomedical Imaging on the Siemens 3T Prisma. Functional and structural scanning parameters are detailed in the **NI Core**. High-resolution structural, fluid-attenuated inversion recovery (FLAIR), diffusion-weighted (DWI), and arterial spin labeling (ASL) perfusion imaging will use in-house standard sequences and will be collected from all participants in session 3. The task-based fMRI sequence will be optimized for an event-related design with a TR of 2 seconds. For the resting-state data, a TR of 0.8 seconds will be used. Task-based and resting-state imaging will be collected in session 4 with varying protocols for participants of SG and CG as described in the timeline below and explicitly detailed in the information and consent form. All MRI sequences will be accompanied by electrical recording of physiological signals from the upper body (e.g., electrocardiogram, electrodermal analyses) to support processing of MRI data and for secondary analyses examining relationships between autonomic nervous system dysfunction, brain, and behavioral outcomes.

D2. TIMELINE

Participants of both groups (stroke, control) will undergo the same protocol, which includes 4 sessions (outlined in the table below).

Session Number	Task Description	Location at Medical University of South Carolina	Approximate Time Commitment
0	Telephone Eligibility Screening 
 • Sensorimotor function screening (Appendix 1) • Cognitive screening (TICS^{26,27}) • MRI Safety Screen 	Via telephone	30 minutes
1	Consent	Stroke Recovery Research Center or remotely through electronic consent	20-30 minutes
2	Multi-system Assessment 
All participants
 
 • Pregnancy Test • EHI[§] • Questionnaires (Appendix 2)[§] • Neuro-Cognitive and emotion Assessment 
Stroke group
 
 • physical Assessment of upper-extremity sensorimotor functioning • NIH-SS 	Stroke Recovery Research Center or partly remotely [§]	3 – 3.5 hours

	
 • SIS[§] 		

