3	
MRI scanning and task familiarization
 
 • MRI Safety Screen • Sleep and vigilance screening 
MRI sequences:
 
 • FLAIR • DWI • ASL • T2* weighted sequence (resting-state) • Physiological recordings 
Learning task:
 
 • Task familiarization (in the mock scanner) 	Center for Biomedical Imaging	2 – 2.5 hours
4	
MRI scanning during task practice
 
MRI Safety Screen
 
Sleep and vigilance screening
 
MRI sequences:
 
 • High-resolution T1 weighted • T2* weighted sequence (task-based) during task practice • Physiological recordings 	Center for Biomedical Imaging	2 – 2.5 hours

D3. DATA ANALYSIS

D3.1 Sample Size Justification.

Given the scarcity of pilot data on stroke and control participants and fMRI-based dynamic connectivity during motor learning, justification has to be based on our best estimates and regarded with some caution. One of the primary goals of this project is to determine effect sizes for the follow-up grant proposal. For changes to latent connectivity characteristics induced by implicit motor learning (pre/post evaluation), empirically obtained effect size estimates were derived from the average effect size of published studies involving participants with chronic stroke⁹ and healthy volunteers⁵⁰. Consequently, sample sizes of 25 and 15 in the stroke survivors and healthy volunteers will allow us to estimate the for the main effect of time (pre/post learning) the within-group effect sizes can be expected to be in the range of 0.33 - 0.52 at 90% confidence level.

D3.2 Analysis Plan.

Imaging Preprocessing. Data will be processed by the CBI Computational Core led by [name]. Preprocessing parameters for the task-based fMRI data will be optimized to fit the requirements of the representational similarity analysis (RSA, described below), specifically smoothing will be reduced to allow for better multivariate pattern detection. Resting-state fMRI data will undergo in-house standard preprocessing.

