For the learning task-based data, a general linear model (GLM) will be fitted to each individual's data serving as the basis for the representational similarity analysis (RSA). In addition to the regressors of interest (matched to the onset time of each regressor of the event-related design of the learning-paradigm: 1st and 2nd order sequence force cues, random force cues) six motion parameters will be included as nuisance covariates. Estimated beta-values will be extracted from the GLM for each stimulus and run for each region of interest (ROI) within subject. For each ROI, a neural matrix will be created by correlating (Pearson) the multi-voxel patterns between all possible combinations of pairs of stimuli of the learning task condition and then averaged across subjects within group (first-order RSA⁵¹). In the second step, group-averaged matrices (only the upper diagonal elements) will be vectorized and correlated (Pearson) for all possible combinations of ROI pairs (second-order RSA⁵¹), which will allow to investigate the representational similarity between ROIs i.e., the clustering/networks of ROIs, with regard to the between-condition similarity in multi-voxel activation patterns.

For the resting-state data, the connectivity analysis will be used to identify physiological biomarkers for recovery and potential predictors for learning efficiency. For this purpose whole-brain resting-state network fluctuations, based on BOLD signal time courses, will be extracted for cortical and subcortical ROIs. Nuisance regression will be performed to account for the effects of motion on functional connectivity (including six translation and rotation parameters from the motion correction transformation, average CSF, white matter, and whole-brain time courses, as well as the first derivatives, squares, and squared derivatives of each of these confound predictors⁵². To extract the dynamic modulation of connectivity over time, time courses will be divided into sub-blocks of multiples of the TR to allow capturing slow-frequency fluctuations by approximating the frequency envelope of the hemodynamic response at the given TR with the highest possible temporal precision. Connectivity will be quantified as the magnitude-squared coherence^{53,54} between each pair of ROI for each sub-block of time⁵⁵. Network characteristics and their temporal dynamics will then be analyzed with dynamic network statistics following the approach given in reference⁵⁵.

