D3.3 Consideration of Sex as a Biological Variable.

While this study will not be sufficiently powered to reveal sex differences, in planned follow-up analyses we will utilize sex as a covariate, as well as age, race, and ethnicity.

D3.4 Potential Challenges and Solutions.

We expect that network definition across participants of the stroke group with varying lesion size and location will be methodologically challenging. Therefore, we will pursue a ROI-based approach in a first step, and we will take an exploratory approach to investigate the influence of lesion location and size on whole-brain networks. As RSA methodology benefits from large sample size, this pilot work includes the conventional univariate analysis of connectivity in its analysis pipeline. The implementation of the RSA analysis pipeline is one of the main purposes of this pilot study even though the results may not provide sufficient power for generalizability.

E. PROTECTION OF HUMAN SUBJECTS

We are committed to conducting safe research that favors benefits over risks. The following sections describe how we will attend to safety and ethical issues involved in conducting the proposed research.

E1. RISKS TO THE SUBJECTS

a. Human Subjects Involvement and Characteristics

As described in section D1, the target sample of the main study will include a total of N=25 adult stroke survivors in the chronic phase, N=15 neurologically healthy adult volunteers, in addition to max. N=8 participants for the initial pilot phase (max. N=4 for stroke and control group).

Inclusion of Women and Minorities.

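### Aim 1 promises a connectivity trajectory over task acquisition, but D3.2 gives the task data only a group-averaged RSA, with no run or time contrast and no participant-level estimate of change

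*Combined protocol and SAP*

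**What the plan says.** **The promise.** Aim 1 sets out to "describe learning-related connectivity changes based on task-based functional magnetic resonance imaging (fMRI") in the stroke and control groups, using a representational modelling approach. It then states its result: "Functional connectivity patterns will be modeled throughout the acquisition phase to capture the temporal trajectory of encoding-related network changes". Aim 2 is to relate these learning-related network dynamics to recovery biomarkers in the stroke group.

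**The data.** The D2 timeline puts the relevant scan in session 4: "T2* weighted sequence (task-based) during task practice".

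**The task analysis.** D3.2 fits a GLM to each individual and extracts betas by stimulus, run and ROI. It correlates the multi-voxel patterns between stimulus pairs within each ROI and averages the resulting matrices over participants in each group (first-order RSA). It then correlates those group matrices between ROI pairs to describe networks of ROIs (second-order RSA).

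**The resting-state analysis.** The next paragraph of D3.2 opens: "For the resting-state data, the connectivity analysis will be used to identify physiological biomarkers for recovery and potential predictors for learning efficiency". The time-resolved method belongs to that paragraph: "To extract the dynamic modulation of connectivity over time, time courses will be divided into sub-blocks of multiples of the TR". Coherence per sub-block and dynamic network statistics follow.

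**The additional analysis.** D3.4 notes that RSA benefits from large samples and that for this reason "this pilot work includes the conventional univariate analysis of connectivity in its analysis pipeline". It says nothing more about that analysis.

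**The concern.** Aim 1's stated result is a change over time within the learning session. The task-data steps carry no time term, and the method that does is assigned to a different scan for a different purpose. An analyst following D3.2 to the letter would reach the end of the task pipeline without having estimated how anything changes as participants learn.

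Three things depend on that estimate.

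- D3.1 gives effect sizes for a follow-up application as a primary goal. A change that is not estimated has no effect size.
- Aim 2 needs a network measure for each stroke participant. Averaging over participants before the ROI-to-ROI step removes it.
- If the gap is filled after the data are seen, the division into runs or blocks, the metric and the contrast are all open to choice.

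**Working it through.** The claim rests on no figure in the plan, so there is none to reproduce. The check maps each analysis step to its data, its level and its use of time.

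| Step | Data | ROI-to-ROI? | Time used? | Level of output |
|---|---|---|---|---|
| GLM betas (D3.2) | task | no | indexed by run | participant |
| First-order RSA (D3.2) | task | no | none stated | group average |
| Second-order RSA (D3.2) | task | yes | none stated | group |
| Sub-block coherence, dynamic network statistics (D3.2) | resting state | yes | yes | not stated |
| Univariate connectivity (D3.4) | not stated | not stated | not stated | not stated |

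**Time.** The run index appears once, when the betas are extracted, and no later step uses it. No specified task-data step models a trajectory. The one time-resolved step is on resting-state data.

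**Participant level.** The main study has 25 + 15 = 40 participants. After averaging within group, each ROI has one matrix per group, so the second-order step gives one coefficient per ROI pair per group: 2 values from 40 people. There is no between-participant variance from which to form a standardised effect. Aim 2 needs 25 individual values in the stroke group, and this pipeline supplies 1 group value per ROI pair. Keeping runs separate would give one value per run per group, which still leaves no participant-level estimate.

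**What pooling runs would do (an assumption; the plan does not say whether runs are pooled).** Let an entry of the first-order matrix in group *g* at run *r* be

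s_g(r) = m + b_g (r − r̄), for r = 1, …, R.

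The deviations from the mean run r̄ sum to zero, so the average over runs is m whatever b_g is. With b = +β in one group and b = −β in the other, both groups pass the same matrix to the second-order step. Opposite learning slopes could not be told apart. The number of runs R is not given, and the result does not depend on it.

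**Whether rest could substitute.** The D2 table lists "T2* weighted sequence (resting-state") under session 3, whereas the imaging section of D1.4 says "Task-based and resting-state imaging will be collected in session 4". These two places must be reconciled. On either reading the resting-state series is a separate sequence from the task-practice scan, so it cannot show connectivity during acquisition.

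**The time contrast in D3.1.** The sample-size section refers to a before/after learning effect. D3.2 has no matching analysis step, and a two-point contrast would not be a trajectory in any case.

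**The case against.** The strongest reply is that second-order RSA is itself an ROI-to-ROI network analysis of task data, and plausibly the representational approach that Aim 1 names. This stands. A reader might infer that the task data receive no connectivity analysis at all, and the documents do not support that. What the second-order step lacks is a time contrast and a participant-level output.

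Second, betas are extracted per run and nothing says runs are pooled. This also stands. A reader might infer that the task data can never give a trajectory, or that groups with opposite slopes will necessarily look identical. Run-wise RSA is compatible with the text, and the masking of slopes follows only if runs are pooled. However, being compatible with the text is not the same as being specified, and the loss of participant-level estimates does not depend on pooling.

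Third, the D3.4 analysis is introduced as a response to the sample size RSA needs, and RSA is applied to task data, so a task-data reading is natural. It would be wrong to say that no such analysis exists. It is undefined, and so cannot be relied on to deliver the Aim 1 result.

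Fourth, this is a proof-of-concept study that admits limited power. That excuses imprecise estimates. It does not explain why the first aim's stated quantity has no estimator.

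Finally, an obvious remedy, coherence per run for each learning mode, may not work. The design is event-related, and D1.4 lets the hidden second-order rule occur within both sequential and random force cues. If modes share runs, one coherence value per ROI pair per run cannot separate them. This objection is accepted and shapes the fix.

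**Conclusion.** The concern holds in this form: D3.2 contains no step that estimates change over acquisition from the task data, and it reserves time-resolved connectivity for rest. The D3.4 analysis does not close the gap because its data set, metric and time resolution are not stated. The consequence is no effect size for Aim 1's trajectory and no individual network measure for Aim 2. This is more than missing detail, because the stated order of operations (average over participants, then relate ROIs) removes the information both aims need.

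No numerical bias can be attached to it. The statement about opposite slopes is conditional on pooling runs. The participant-level conclusion rests only on the averaging step as written. The data themselves are not deficient: the betas already planned per run are enough to build the missing analysis.

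**What to change.** In D3.2, for the session-4 task data:

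- Compute first- and second-order RSA per participant and per run (or per early and late block), separately for first-order, second-order and random cues where the stimuli allow. Do not average over participants before the ROI-to-ROI step.
- Name as the Aim 1 analysis a model of similarity on group × run with participant random effects. Use its participant-level estimates as the network input to Aim 2.
- State that the D3.4 univariate connectivity analysis is applied to the task runs, by run, and give its metric.
- Claim mode-specific connectivity only if runs or blocks separate the modes, or if a condition-specific connectivity model is used.
- State the number of runs and how they divide the acquisition phase.
- Reconcile the session in which resting-state data are acquired.

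The cost is plan text and analyst time. If the resting-state coherence method is reused, it must be adapted from a TR of 0.8 s to the task TR of 2 s. Participant-level, run-wise similarities will be noisier than group averages, so the group-averaged RSA can stay as a descriptive summary. No additional scanning is needed.
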